10.2 ABBREVIATIONS AND SPECIAL TERMS

AE	adverse event
----	---------------

AHRQ CAHPS	Agency for Healthcare Research and Quality, Consumer Assessment of Healthcare Providers and Systems
AUDIT-C	3-item Alcohol Use Disorder Identification Test – Consumption
BHC	behavioral health consultant
BHP	behavioral health psychotherapist
CC	collaborative care
CC-COD	collaborative care for COD
CFR	Code of Federal Regulations
CA	California
CMP	clinical monitoring plan
CLARO	Collaboration Leading to Addiction Treatment and Recovery from Other Stresses
COD	co-occurring disorder
CRF	case report form
DSMB	Data Safety Monitoring Board
DSMP	Data Safety Monitoring Plan
EHR	electronic health record
EUC	enhanced usual care
FCCH	First Choice Community Healthcare
FDA	Food and Drug Administration
FQHC	Federally qualified health centers
GCP	good clinical practice
HCA	Hepatitis C virus
HH	Hubert Humphrey
HIPAA	Health Insurance Portability and Accountability Act
HMS	Hidalgo Medical Services
HPSA	health professional shortage area
ICH	International Council on Harmonization
LACDHS	Los Angeles County Department of Health Services
IRB	Institutional Review Board
MDD	major depressive disorder
MH	mental health
MI	Motivational interviewing
MV	Mid Valley Comprehensive Health Center
MOP	Manual of Procedures
MOUD	medications for opioid use disorder
NCT	National Clinical Trial
NIH	National Institutes of Health
NIMH	National Institute of Mental Health
NM	New Mexico
NSDUH	National Survey on Drug Use and Health
OHRP	Office for Human Research Protections
OD	opioid use disorder

OV-ERI	Olive View Education and Research Institute
PC-PTSD-5	Primary Care PTSD 5-item checklist
PCL-5	Posttraumatic stress disorder checklist for DSM-5
PCP	primary care provider
PHQ-9	Patient Health Questionnaire for Depression – 9 item
PI	Principal Investigator
PROMIS	Patient-Reported Outcomes Measurement Information System
Providence	Providence Health & Services – Southern California
PST	problem solving therapy
PTSD	posttraumatic stress disorder
RA	Research Assistant
RAB	Research Advisory Board
RCT	randomized clinical trial
SAE	serious adverse event
SAP	Statistical Analysis Plan
SDCC	Statistics and Data Coordinating Center
SFC	San Fernando Health Center
SRG	Survey Research Group
SRMC	Sandoval Regional Medical Center
SUMMIT	Substance Use Motivation and Medication Integrated Treatment
UNM	University of New Mexico
UP	unanticipated problem
ViStA	Violence and Stress Assessment
VR-12	Veterans RAND 12-item Health Survey
WET	Written Exposure Therapy

10.3 PROTOCOL AMENDMENT HISTORY

The table below is intended to capture changes of IRB-approved versions of the protocol, including a description of the change and rationale. A **Summary of Changes** table for the current amendment is located in the **Protocol Title Page**.

Version	Date	Description of Change	Brief Rationale
2.0	10/12/20	
We amended the Protocol in major ways to include the activities which will occur as part of our newly funded Competitive Revision (CR). The amended protocol additionally includes some minor changes to the parent study. We include the
 
CR in the amended protocol under guidance from our project officer, [name] and because the CR and the parent study are operationally tied together. Thus, for NIMH DSMB review, we have provided one unified protocol that includes all components.
	
There are 3 main reasons for these changes: (1) to add information about the CR, (2) to insure compatibility with changes requested from RAND’s Institutional Review Board, and (3) because additional discussion among our team led to greater clarity in describing procedures.

3.0	2/3/21	
We responded to queries about circumstances warranting termination (#4 in memo), stopping rules (#6 in memo), and protocol deviations/violations (#9 in memo). We also added a paragraph explaining how the PHQ works across the eligibility screener and the baseline interview.
	
To be responsive to the board and to describe a change in screening that was approved by [name].

4.0	3/15/21	
We made changes to the Statistical Considerations section (section 9) in accordance with DSMB queries
	
Most changes in this amendment were made in response to DMSB queries or

		
about statistical power and other points of analysis. We clarified language around reporting of AEs, SAEs, protocol deviations, and unanticipated problems. We added additional detail about Care Coordinator training and supervision, updated the eligibility criteria to indicate that participants cannot be receiving both MOUD and psychotropic medication from an external provider prior to study enrollment, and updated the eligibility screener to include the PHQ-8 rather than PHQ-9. Finally, we made some minor wording changes to maintain internal consistency within the protocol.
	
to increase internal consistency and clarity of procedures described in the protocol. Eligibility criteria were updated to ensure that participating patients are in a position to receive COD care coordination at their primary care clinic. We changed the PHQ-9 to the PHQ-8 at eligibility screening to avoid asking for information that could require us to break confidentiality before a participant has completed the informed consent process.

5.0	6/24/21	
We added First Choice Alameda to tables 5.1 and 5.3 of clinic-level characteristics/data. Please note that at this time we are still waiting for our clinic partners to provide us with some of the specific site characteristics, so some fields for Alameda are blank. We changed the number of clinics from 13 to 14.
	
The study added a new site, First Choice Alameda to the trial.

6.0	12/9/21	
We updated throughout to indicate that we have two more clinics in a new health system, CSV: Baker Street Village and Kern River. We increased the number of clinics from 14 to 16 throughout. We removed MDD and PTSD remission/response, opioid overdose risk behaviors, and general health functioning outcomes as secondary outcomes.
	
To boost recruitment, we have added a new health system in central California – Clinica Sierra Vista. We may add more CSV sites after we onboard the first two. We revised the outcomes to boost power.

6.1	1/26/22	We changed the number of clinics from 14 to 16 and added a new health system, Clinica Sierra Vista.	We did this to boost recruitment.
6.2	3/22/22	
We removed Clinica Sierra Vista and added two new health systems in Los Angeles County, California (Providence & HH).
 
We doubled the patient incentive amount for the baseline survey and added a \$25 bonus incentive to encourage same day or call-back later completion.
	
These new health systems were recently engaged to replace the systems we lost.
 
To boost patient enrollment.

6.3	5/27/22	
We updated the study timeline.
 
We added information explaining the addition of the California clinics.
 
We added information about the process for reportable events at participating California clinics, and we made other minor changes to clarify information for the new California sites.
	
To account for recruitment challenges and addition of new clinical sites.
 
To provide a rationale for our selected study sites.
 
Changes made per the request of partnering California clinics.

		We updated [name] institutional affiliation to be the University of Pittsburgh.	[name] moved from UNM to the University of Pittsburgh.
7.0	7/29/22	
We added information detailing RAND taking over data collection from UNM.
 
The parent and supplement (CLARO+) consents (dated 7/21/2022) were updated with new contact information to reflect the SRG transition and allow the SRG to receive patient contact information, as well as added language clarifying which study incentives may be in the form of cash and which may be in the form of a merchandise card. Additionally, a sentence specifying that the study may collect mortality data from the state vital records office was added, which will allow us to collect mortality data from California. The protocol contained all of these changes, as well as a few minor staffing changes and a sentence on the patient demographics at the Providence clinics.
	To provide details on the transition from UNM to RAND in anticipation of the change in data collection activities
8.0	10/5/22	Added details on the transition from parent to supplement at various clinics	To account for updates in recruitment status and provide a realistic explanation of transitioning from CLARO to CLARO+

9.0	10/11/22	Added Mid Valley Comprehensive Health Center and San Fernando Health Center to the study, clarified the parent system for these new clinics, and rectified some mislabeling of clinic numbers from previous iterations of the protocol	To boost recruitment
10.0	01/13/23	Changed name of PSJ to Providence Health & Services– Southern California	To include a wider net of PSJ clinics and hopefully boost recruitment.
11.0	05/26/23	End of recruitment at PSJ was noted. We also noted that some patients who are receiving primary care at UNM may be referred to the study from UNM providers outside of the three UNM clinics. Changed duration of study recruitment period to reflect extended recruitment period.	To transition study resources to a site that will likely be more productive for recruitment and enrollment, and to increase potential for study recruitment. To provide additional time to meet the target sample size.
12.0	06/14/23	JWCH Institute Inc. was added as a participating healthcare system, and end of recruitment at PSJ was noted.	To transition study resources to a site that will likely be more productive for recruitment and enrollment, and to increase potential for study recruitment.
13.0	6/27/23	Added Sandoval Regional Medical Center (SRMC) as an additional recruitment site in New Mexico. SRMC is part of the UNM system.	To increase potential for study recruitment.

1.1 SAP Details

Statistical analysis plan (SAP) for Randomized Controlled Trial Comparing Collaborative Care and Enhanced Usual Care for Patients with Co-occurring Opioid Use Disorders and Depression and/or Post-traumatic Stress Disorder (PTSD). The study is referred to as CLARO (Collaboration Leading to Addiction Treatment and Recovery from Other Stresses) and is also referred to as the parent study.

On 8/31/2022 a Competitive Revision (CR—CLARO+) was awarded to enroll additional patients into an additional study arm. CLARO+ adds additional clinical interventions used by the care coordinator to the Collaborative Care Model being tested by CLARO.

Because the CR did not enroll sufficient individuals to allow for separate analyses, in consultation with our Research Advisory Board, the NIMH scientific officer and the NIMH project officer, it was decided to combine patients enrolled into the parent study intervention arm, with patients enrolled into the CLARO+ study intervention arm for all analyses. The justification for this was that the objective of the trial was to test the Collaborative Care Model for individuals with co-occurring disorders, and the model was identical across both the CLARO and CLARO+ trials.

This SAP describes analyses for patients enrolled into both CLARO and CLARO+.

National Clinical Trial Identified Number: NCT04559893 (CLARO).

National Clinical Trial Identified Number: NCT04634279 (CLARO+)

Protocol Version Number: 13.1

1.2 SAP Revisions

SAP revision history is summarized below, with a summary of changes from previous versions listed first.

SAP Date	Summary of Revisions Made	Rationale
11/15/24	
Revised secondary and exploratory outcomes including:
cut MOUD initiation and engagement measuresmodified continuity of care and MOUD access to be buprenorphine-specific	
Tailor analyses based on time/budget constraintsEnsure all design and analysis descriptions reflect latest knowledge and assumptions (e.g., actual sample size, best practices, data limitations,

	
 modified definitions of access to treatment and quality of care secondary outcomes modified drug use frequency secondary outcome to be opioid use frequency created alcohol use, drug use frequency, opioid use severity, and opioid overdose risk behaviors exploratory outcomes added stimulant use frequency as an exploratory outcome Cut all-cause mortality analysis Revised baseline characteristic specifications (Table 5) Added plans to combine parent study and competitive revision (CR) samples, and revised text describing CR accordingly Added details on model covariates (prior MOUD and site variable) specifications to account for potential small sample sizes Revised power calculations with final enrollment numbers, parent study and CR combined samples, and modified outcomes Updated moderators and mediators Modified methods for handling missing data in the baseline and follow-up surveys. Added detail on non-response weight calculations, including criteria for determining if non-response weights are necessary 	resource constraints, etc.) prior to unblinding
06/25/23	
 Edited specifications of two primary outcomes (MOUD access and continuity of care) 	
 Original, planned, MOUD outcomes were deemed not possible to calculate due to limitations of the EMR data
02/16/21	
 Addition of detailed description of the statistical models to be used, 	
 Address queries from 09/14/20 DSMB meeting

	
including approach for handling missing follow-up data
 
 • Modification of primary and secondary analyses and removal of analyses that leveraged repeated measures • Updated power calculations to utilize a simulation-based calculation • Addition of a description of the composite statistical hypothesis 	
--	--	--

2 Introduction

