Supplement	3	3	3	3	3	3	3	0	0	0	0	0	0	0	0	0	0
PSJ																	
Parent	1	1	1	1	1	1	1	1	0	1	1	0	0	0	0	0	0
Supplement	0	0	0	0	0	0	0	0	0	0	0	1	1	1	1	1	1
HMS																	
Parent																	
	12	12	12	18	18	18	18	15	0	15	15	15	15	15	15	15	15
TOTAL PARENT																	
TOTAL SUPPLEMENT																	
TOTAL ENROLLED																	

Table 5.3 (Part 2) – 2/27/2023 through 5/22/2023

	2/27/2023	3/6/2023	3/13/2023	3/20/2023	3/27/2023	4/3/2023	4/10/2023	4/17/2023	4/24/2023	5/1/2023	5/8/2023	5/15/2023	5/22/2023	Total New	Total Previous	Combined Total	3 Mo Fu Complete (70%)	6 Mo Fu Complete (60%)
HHH+MidValley Sites																		
Parent	12	12	12	12	12	0	0	0	0	0	0	0	0	234	5	239	167.3	143.4
Supplement	0	0	0	0	0	12	12	12	12	12	12	12	12	96	0	96	67.2	57.6
														330	5	335	234.5	201
UNM																		
Parent	0	0	0	0	0	0	0	0	0	0	0	0	0	18	251	269	188.3	161.4
Supplement	2	2	2	2	2	2	2	2	2	2	2	2	2	40	0	40	28	24
														58	251	309	216.3	185.4
FCCH																		
Parent	0	0	0	0	0	0	0	0	0	0	0	0	0	0	329	329	230.3	197.4
Supplement	0	0	0	0	0	0	0	0	0	0	0	0	0	21	25	46	32.2	27.6
														21	354	375	262.5	225
PSJ																		
Parent	0	0	0	0	0	0	0	0	0	0	0	0	0	10	0	10	7	6
Supplement	1	1	1	1	1	1	1	1	1	1	1	1	1	19	0	19	13.3	11.4
														29	0	29	20.3	17.4
HMS																		
Parent														0	35	35	24.5	21
	15	15	15	15	15	15	15	15	15	15	15	15	15	438				
TOTAL PARENT															620	882	617.4	529.2
TOTAL SUPPLEMENT															25	201	140.7	120.6
TOTAL ENROLLED															645	1083	758.1	649.8

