3. A 2 point reduction in depression symptoms (PHQ-9). This provides power to detect effects below the clinically important difference for individual change of 5 points.²²⁵
4. A 3.5 point reduction in PTSD symptoms (PCL-5). A previous study of delivering PTSD treatment in primary care setting to active duty military found a reduction in PTSD symptoms of 7 points.²²⁶

Prior to breaking the study blind but after completion of data collection, the above distributions and power calculations were updated in the SAP to reflect observed data.

Dropout is of minimal concern in this study, as all analyses are intention-to-treat. For the outcomes based on self-reported symptoms, i.e. depression symptoms and PTSD symptoms, we expect a 20% loss to follow up. This loss to follow up has been accounted for in the power calculations.

The sample size provides sufficient power for secondary outcomes. Details are included in the SAP.

Original Sample size considerations for CR:

Figure 4.2 (above in Section 4.2) illustrates the sample sizes in each arm and in each phase of the study, along with a conceptual representation of the revision analyses. A total of 900 individuals will be randomized between CC-COD and EUC (Phase I) and a total of 300 individuals will be randomized

between CC-COD+ and EUC (Phase II). Based on data from the INSPIRE study, we assume 80% of patients have SPs who are willing to participate in treatment and that the effect of CC-COD+ for the 20% of patients without SPs willing to participate will be the same as CC-COD. Using the same assumptions for the power calculations as above, we have 80% power to detect an incremental effect of CC-COD+ over CC-COD on the number of days of continuous MOUD care of 14 days. A growing body of evidence suggests the mortality is lower during OUD treatment, and that mortality is increased in the first four weeks after treatment cessation.¹³⁵ Two weeks of additional OUD treatment reflects a clinically significant increase in the duration of treatment given these known mortality patterns after treatment cessation. The sample size for the CR was determined based on this clinically meaningful effect size.

As noted elsewhere, it was later decided to combine the CR and parent study populations for all analyses. This decision was made in consultation with our Research Advisory Board, the NIMH scientific officer and the NIMH project officer due to lower than expected recruitment.

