2.6 Study design

This study is a stratified randomized trial testing CC-COD versus EUC, with strata defined by prior MOUD exposure and primary care clinic.

As part of the CR, we initially planned to compare CC-COD+ to CC-COD, with MOUD continuity of care as the primary outcome. However, despite sustained and targeted efforts, recruitment was lower than expected, and we did not reach our targeted enrollment goals for either CC-COD or CC-COD+. Based on input from our research advisory board and NIH project officer, we now plan to combine the CC-COD and CC-COD+ samples when analyzing the data for additional information about the potential effectiveness of the intervention. Since the Collaborative Care Model is identical across both trials, and the only difference between the arms is in the additional clinical modules supported by CC-COD+, combining the active CC-COD and CC-COD+ arms for an exploratory analysis should provide additional precision around the estimated treatment effect for CC-COD/CC-COD+.

The study's original target sample size was 900, with an additional 300 patients targeted for the CR, for a combined target of 1200. Our final sample size was 797 (729 following the original protocol and 68 following the protocol from the CR). This analysis plan has been modified to include actual final power calculations calculated prior to breaking the blind but after all data collection ended.

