3.4.2 Overview and General Principles

The primary analyses will be performed for the intention-to-treat population, which consists of all randomized subjects. All individual statistical hypotheses will be tested using two-sided tests, with adjustment for multiple testing using a Bonferroni or Benjamini-Hochberg correction. Primary outcomes will be analyzed at a Type I error rate of 1.25% to control the family-wise error rate at 5% (e.g., so $0.05/4=0.0125$ when using a Bonferroni correction or the first p-value threshold for significance with Benjamini-Hochberg). Similarly, secondary and exploratory outcomes will be analyzed at Type I error rates to control family-wise error rate at 5% within domain. See Table 2 and 3 for definition of secondary outcome domains and our exploratory outcomes.

Outcomes derived from the follow-up surveys are subject to nonresponse, and statistical hypotheses based on these outcomes will be tested using nonresponse weighted models, if necessary. Traditionally, a logistic regression model can be specified predicting response using the demographic characteristics listed in Table , the baseline characteristics listed in Table , and the randomized treatment assignment. The model is given by:

$$\log \left(\frac{\Pr(R_{ij}=1)}{1-\Pr(R_{ij}=1)} \right) = \eta_j + \mathbf{X}_{ij} \boldsymbol{\theta} + \gamma T_{ij} + \rho P_{ij}$$

where η_j represent health system fixed effects. The nonresponse weight for participant i in health system j is given by $w_{ij} = \frac{1}{p_{ij}}$, where $p_{ij} = \Pr(R_{ij} = 1)$. However, we will utilize a nonparametric machine learner to estimate our nonresponse weights to allow for more complex relationships between the predictors variables and the odds of being a responder, thereby producing more high-quality nonresponse weights if they are deemed necessary.

To assess whether there is a need for use of nonresponse weights in our final analyses, we will assess how representative our sample of responders is for each outcome using effect sizes (ES) differences. If most of the ES differences are small (e.g., less than 0.1 or 0.2), we will feel good about the representativeness of our sample of responders to the original baseline sample and not utilize nonresponse weights in our final analyses.

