3.5 Statistical power

All calculations are for 80% power at a Type I error rate of 1.25%, which accounts for the multiple primary outcomes using a Bonferroni correction to control the family-wise error rate at 5% ($0.05/4 = 0.0125$). Actual calculations use the observed loss to follow up rate in the final sample.

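### The primary PHQ-9 and PCL-5 analyses leave the collected 3-month scores unused, although about 34% of randomised participants lack 6-month survey data; an analysis using both visits should be added.

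*SAP*

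**What the plan says.** - **Collection.** The Protocol's schedule of activities (1.3) and section 8.1 place PHQ-9 and PCL-5 at baseline, 3 and 6 months.
- **Endpoint and model.** SAP Table 1 (2.5.1) defines both symptom endpoints as the 6-month score. SAP 3.4.4 fits one linear regression on health system, prior MOUD and arm. Neither the baseline nor the 3-month score enters it.
- **Missed surveys.** SAP 3.4.1 defines response by the 6-month survey only. SAP 3.4.2 describes a model "predicting response using the demographic characteristics listed in Table" and further baseline characteristics, plus arm, health system and prior MOUD, with a machine learner to be used in practice. The weights are not used if most baseline effect-size differences between responders and the full sample fall below about 0.1 or 0.2.
- **Imputation.** In SAP 3.4.2, single or multiple imputation is for items missing within completed surveys, not for a survey never completed.
- **Use of 3-month data.** The only analysis use I found is for the mediators in SAP 3.4.7 (care experience and working alliance). The only sensitivity analysis I found is the one restricted to CC-COD (SAP 3.2).
- **History.** SAP 1.2 lists, under 02/16/21, the "removal of analyses that leveraged repeated measures" and gives DSMB queries as the reason. That entry dates the change; the point rests on the current sections above.
- **Sample.** SAP 2.6: "Our final sample size was 797". SAP Table 9 shows N=525 (523 for two outcomes) for survey outcomes defined in all participants.

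**The concern.** Analysing by randomised arm settles how people are grouped; it does not supply a score for someone not interviewed at 6 months. The last symptom score before loss is likely to be informative about the missing one, and the plan has it for anyone seen at 3 months but not at 6. Weights built from baseline variables cannot adjust for drop-out driven by what happened after randomisation. The check that decides whether weights are needed looks only at baseline balance, so it could pass while drop-out tracks 3-month symptoms. If the weights are dropped, the analysis becomes an unweighted comparison of 6-month responders with no symptom history in the model.

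Differential drop-out is plausible because participants know their assignment and study Care Coordinators are assigned only in the intervention arm (Protocol 6.3). Two of the four primary endpoints are exposed.

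**Working it through.** **1. Loss at 6 months.** Randomised 797 (SAP 2.6); 6-month survey data 525 or 523 (SAP Table 9).
1 - 525/797 = 34.1%; 1 - 523/797 = 34.4%. The Protocol's planning figure was 20% (9.2).

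**2. Reproduce the SAP's detectable effects.** Inputs: "All calculations are for 80% power at a Type I error rate of 1.25"%, two-sided (SAP 3.4.2), 1:1 allocation (SAP 2.7). SDs and Ns are from SAP 3.5.1.
MDE = (2.498 + 0.842) × SD × sqrt(4/N), with the sum 3.339 after rounding.
- Depression: 3.339 × 6.6 × sqrt(4/405) = 2.19 (2.20 with the t distribution). SAP: 2.2.
- PCL-5: 3.339 × 17.8 × sqrt(4/368) = 6.20 (6.22 with t). SAP: 6.23.

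Both reproduce, which confirms that the power section counts only people with 6-month data.

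**3. Precision gained by adding 3-month scores.** The documents give neither the number seen at 3 months only nor the 3-to-6-month correlation (rho), so both are assumed. For a likelihood analysis with monotone missingness,
1/N_eff = (1 - rho²)/n6 + rho²/(n6 + n3only).
The enrolled subgroup size is also assumed, by applying whole-sample retention: 405/(525/797) = 615 for depression and 368/(525/797) = 559 for PTSD. Take rho = 0.65 (rho² = 0.4225).
- Depression, 8% (49 people): 0.5775/405 + 0.4225/454 gives N_eff of about 424; MDE 2.14.
- Depression, 15% (92 people): 0.5775/405 + 0.4225/497 gives about 439; MDE 2.10.
- PCL-5, 8% (45 people): 0.5775/368 + 0.4225/413 gives about 386; MDE 6.05.
- PCL-5, 15% (84 people): 0.5775/368 + 0.4225/452 gives about 399; MDE 5.95.

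Over a wider range (5-15%, rho 0.4-0.7), depression N_eff is about 410-446 (MDE 2.18-2.09) and PCL-5 N_eff about 372-405 (MDE 6.16-5.91). The gain in detectable effect is about 1-5%.

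As a plausibility check on the share, Protocol Table 5.3 has columns headed "3 Mo Fu Complete (70"%) and "6 Mo Fu Complete (60"%). If those forecasts were realised, at least 10% would have a 3-month but no 6-month interview.

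**4. Bias, illustration only.** Let w be the 3-month-only share among people with any follow-up score. Let g be the between-arm difference, in SD units, in how far those people depart from completers at 3 months. The completers-only contrast then shifts by about w × rho × g × SD.
- Low end: w = 0.05/(0.6587 + 0.05) = 0.0706, rho 0.5, g 0.2. Shift 0.05 PHQ points or 0.13 PCL-5 points.
- High end: w = 0.15/(0.6587 + 0.15) = 0.1855, rho 0.7, g 0.5. Shift 0.43 PHQ points or 1.16 PCL-5 points.

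That is 2-20% of the SAP's detectable effects. Every input except the SDs and the retention fraction is assumed. With g = 0 the shift is zero.

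**The case against.** **What stands.** Bias in a between-arm contrast needs selection that differs by arm; similar selection in both arms largely cancels. The documents show no such difference. The precision gain is small and rests on assumed inputs. The remedy also reaches a minority of those lost: with 8-15% seen at 3 months only, 26.1% to 19.1% of participants have neither score, which is 77% to 56% of the 34.1%. For them, baseline information is all there is, and the SAP's weights do use it. Weighting and mixed models are both legitimate missing-at-random methods, and the simplification answered DSMB queries that are not reproduced in the documents.

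**Stronger readings a reader might infer, which the documents do not support.**
- *That the Protocol dismisses loss on the symptom scores.* Section 9.2 does say "Dropout is of minimal concern in this study, as all analyses are intention-to-treat", but it then treats the self-reported symptom outcomes separately ("we expect a 20% loss to follow up") and builds that loss into the power calculation. Section 9.4.2 plans weighted models for these two endpoints.
- *That Table 5.3 is a rival planned loss of 40%.* It is a mid-trial enrolment and completion forecast, not a design assumption.
- *That power still rests on 20% loss.* SAP 3.5 uses the observed numbers.
- *That 34% is the loss in the depression and PTSD analyses.* It is for all participants; the subgroup denominators are not given.

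**What does not answer the point.** None of this explains leaving out a relevant score already in hand. Moreover, Protocol 9.4.2 describes weighting without the condition that the SAP attaches, so the safeguard in force is weaker than the Protocol suggests.

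**Conclusion.** The point holds as a gap in the handling of missing outcomes on two primary endpoints. The current text uses 6-month responders only, adjusts for non-response from baseline variables and arm if at all, and leaves the 3-month PHQ-9 and PCL-5 scores unused in the face of about 34% overall loss. It has not been shown that the planned estimate is biased. What is shown is that drop-out related to 3-month symptoms and differing by arm would be neither detected nor corrected.

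On the central assumptions the depression detectable effect improves by about 2-4%, so precision alone would not justify the change. The case rests on protection against bias of a size that cannot be computed from the documents. Using the 3-month score would not remove bias from drop-out driven by symptoms that arise after 3 months. The addition is worthwhile and cheap; it does not invalidate the planned analysis.

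**What to change.** 1. Keep the 6-month between-arm contrast as the estimand for both endpoints.
2. Add to SAP 3.4, at least as a sensitivity analysis, either a mixed model on the 3- and 6-month scores (arm by visit, adjusted for baseline score, health system and prior MOUD) or multiple imputation of the missing 6-month score that includes the baseline and 3-month scores, by arm.
3. Report by arm, within the probable-depression and probable-PTSD subgroups, the number enrolled, seen at 6 months, seen at 3 months only, and seen at neither. Give the 3-month scores of those later lost beside those retained.
4. Reconcile the unconditional weighting in Protocol 9.4.2 with the conditional rule in SAP 3.4.2.

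Cost: SAP wording, one additional model per endpoint and one table, from data already scheduled for collection. If treatment assignment has already been opened to the analysts, label the addition post hoc.
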